10.1. Primary Efficacy Analysis

The primary endpoint is the Day 180 global disability assessed via the ordinal modified Rankin score (mRS).

The null hypothesis is that the cumulative odds ratio for mRS at 180 days in the MIS group compared to MM group is less than or equal to 1. The alternative hypothesis is that the cumulative odds ratio for mRS at 180 days is greater than 1. Formally, the null and alternative hypotheses to be tested are as follows:

H0: OR ≤ 1

HA: OR > 1 ,

where OR is the cumulative odds ratio for the mRS at the 180-day follow-up visit, with higher values indicating better outcomes in the MIS group.

Statistical analysis of the primary endpoint will be conducted using a logistic regression analysis of the 180-day mRS scores. The primary efficacy endpoint is met if the overall treatment effect is positive at a one-sided alpha of 0.02. The odds ratio and corresponding 95% confidence interval will be estimated from the proportional odds model. The proportional odds assumption will be assessed visually for the cumulative proportions and odds ratio estimates. The primary analysis will be unadjusted. A secondary analysis model will include the minimization variables of Hemphill Score and hemorrhage location. The mRS scores of 5 and 6 will be combined into a single group for the purposes of endpoint evaluation. Subjects deceased during study follow-up will be scored as mRS 6. As a sensitivity analysis, the mRS scores of 5 and 6 will be evaluated as separate groups.

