10.1 Sample Size Estimation for the Primary Outcome

The proposed study is a randomized controlled study designed to demonstrate the efficacy of MIS to improve clinical outcomes across the entire population of patients with supratentorial ICH, as well as to evaluate effect sizes within major anatomical sub-groups (e.g., deep vs. lobar hemorrhage) and cohorts (e.g. age, presenting GCS). In addition, the treatment arm will provide, for the first time, a prospective, independently adjudicated, characterization of the technical outcomes and complication rates associated with the Artemis MIS procedure.

This design provides 81% power for a cumulative odds ratio of 1.7 for the Day 180 mRS. The design's overall one-sided Type I error rate is 2.5%.

The maximum study sample size is 500 subjects and the minimum sample size is 200 subjects. The final study sample size is estimated to be low if the treatment effect is small and the study could be stopped for futility or if the treatment effect is large and the study could be stopped for expected success. The final study sample size will be high if the evidence for the treatment effect is inconclusive.

The Day 180 mRS distribution used for sample size estimation was based on control arm data from the following published studies: MISTIE⁴⁸, STICH¹³, and SICHPA⁶⁴. The distribution of mRS functional outcomes utilized in the sample size estimation is provided in Table 3.

Table 3. Distribution of mRS Functional Outcomes

mRS Distribution	0	1	2	3	4	5/6
MM	3%	10%	7%	7%	14%	59%
MIS	5%	15%	10%	9%	16%	46%

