Statistical Analysis Plan

For CLP 11899

MIND: A Prospective, Multicenter Study of Artemis a Minimally Invasive Neuro Evacuation Device, in the Removal of Intracerebral Hemorrhage

Prepared by: Penumbra Inc.

NCT number: NCT03342664

Date: January 02, 2020

1. Overview

This is a multi-center randomized controlled study designed to compare the safety and efficacy of minimally invasive hematoma evacuation with the Artemis Neuro Evacuation Device to best medical management for the treatment of intracerebral hemorrhage (ICH).

Up to 500 patients will be enrolled from up to 50 global centers (US and OUS). Each site will be limited to a maximum enrollment of up to 120 patients (~20% of total enrollment).

This Statistical Analysis Plan (SAP) will provide details to further elaborate statistical methods as outlined in the protocol and will describe analysis conventions. The SAP will be signed off prior to unblinding.

2. Sample Size

A sample size of up to 500 patients was selected for this study. Based on simulations, this trial has 81% power for a cumulative odds ratio of 1.7 with a one-sided alpha of 0.025. The minimum sample size is 200 patients (approximately 133 MIS and 67 MM).

The Day 180 mRS distribution used for sample size estimation was based on control arm data from the following published studies: MISTIE II (Hanley 2016), STICH (Mendelow 2005), and SICHPA (Teernstra 2003). The distribution of mRS functional outcomes utilized in the sample size estimation is provided in Table 1.

Table 1. Distribution of mRS functional outcomes

mRS Distribution	0	1	2	3	4	5/6
MM	3%	10%	7%	7%	14%	59%
MIS	5%	15%	10%	9%	16%	46%

3. Randomization

Randomization takes place centrally through a commercially available Interactive Web Response System (IWRS). Randomization will occur in a 2:1 ratio to either MIS or MM. The treatment allocation will be balanced by Hemphill Score (0-2, 3-4) and hemorrhage location (primarily lobar, primarily deep).

If a lack of equipoise for randomization between treatment and control occurs during trial execution, the trial randomization assignment will be revised to randomize all patients to the MIS. The minimum sample size for patients assigned to MIS treatment is 133 patients.

4. Interim Analysis

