Interim data analysis of the primary efficacy and safety endpoints is planned after 200 subjects have been enrolled. Additional interim analyses will be conducted after every 50 subjects. The interim analyses will include imputing the 180-day mRS score for subjects who do not have 180 day scores. Based on the predictive probability that the study would be a success, the study may be stopped early for futility or enrollment may be stopped based on expected success. The specific mathematical details of the planned analyses are described in the adaptive design report.

If a lack of equipoise for randomization between treatment and control occurs during trial execution, the supplemental adaptive design report provides the details to evaluate the superiority of MIS as compared to the combined MM arms of the MIND trial and any publicly available trial results with randomized MM arms.

5. Decision Rules for Adjusting the Sample Size

The maximum study sample size is 500 subjects and the minimum sample size is 200 subjects. The final study sample size is estimated to be low if the treatment effect is small and the study could be stopped for futility or if the treatment effect is large and the study could be stopped for expected success. The final study sample size will be high if the evidence for the treatment effect is inconclusive. The specific decision rules for sample size adjustments are described in the adaptive design report.

6. Analysis Populations

All primary and secondary effectiveness endpoints will be performed for both the intent-to-treat (ITT) population and per-protocol (PP) population.

- 6.1. Target Population: The target population is patients 18-80 years of age who have a diagnosis of spontaneous, non-traumatic, intracerebral hemorrhage (ICH) ranging in volume between and including 20 and 80 cc, with an associated significant neurological deficit (NIHSS > 6) who do not require emergent open surgical decompression related to uncontrolled intracranial pressure or mass effect.
- 6.2. Intent to Treat Sample: As the primary analysis, all efficacy and safety outcome measures will be analyzed under the intent-to-treat (ITT) principle. Under this principle, the evaluable sample includes all subjects who are randomized. Each subject will be analyzed according to the treatment group to which they were randomly assigned at the time of randomization. This population is the primary population for all efficacy parameters.

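### The primary odds ratio and 95% CI are specified as if N were fixed, although six interim looks can stop enrollment; under assumed thresholds the interval covers about 93% at OR 1.7, mainly because of futility stops

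*SAP*

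**What the plan says.** **Estimate and interval.** SAP 10.1, and Protocol 10.7 in the same terms: "The odds ratio and corresponding 95% confidence interval will be estimated from the proportional odds model". The primary model has no covariates, and mRS 5 and 6 form one category.

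**Sample size.** SAP 5: "The maximum study sample size is 500 subjects and the minimum sample size is 200 subjects".

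**Looks.** SAP 4: "Interim data analysis of the primary efficacy and safety endpoints is planned after 200 subjects have been enrolled" and "Additional interim analyses will be conducted after every 50 subjects". That places looks at 200, 250, 300, 350, 400 and 450. At each, based on predictive probability, "the study may be stopped early for futility or enrollment may be stopped based on expected success". The thresholds and mathematical details are left to the adaptive design report.

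**Test.** SAP 10.1: "The primary efficacy endpoint is met if the overall treatment effect is positive at a one-sided alpha of 0.02". Protocol 10.1: "The design's overall one-sided Type I error rate is 2.5" percent. So the level of the test allows for the looks.

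**Not stated.** Neither document mentions a bias-adjusted OR or an interval that accounts for the looks. SAP 10.4 makes no multiplicity adjustment to the primary comparison. The sensitivity analyses in SAP 13 all concern missing Day 180 scores.

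**The concern.** When N is chosen from the accumulating treatment effect, the model estimate is no longer centred on the truth and a nominal 95% interval need not cover 95%. The plan allows for this in the test but, as far as these documents show, not in the estimate or interval.

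The OR and its limits are how readers will judge the size of the benefit, and the lower limit is read as the smallest plausible benefit. Two distinct effects are possible. A futility stop happens when the running estimate is low, and then reports an OR that is too small. An expected-success stop happens when it is high, and then reports an OR that is too large. If no method is named in advance, the choice of estimator could be made after the result is known.

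**Working it through.** **Inputs from the documents.** MM distribution 3, 10, 7, 7, 14, 59% (SAP Table 1); OR 1.7; 2:1 allocation; maximum N 500; final one-sided level 0.02 (z = 2.054); six looks. Applying OR 1.7 to the MM row gives 5.0, 15.3, 9.6, 8.8, 15.6, 45.8%, which agrees with the MIS row of Table 1 to rounding.

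**Assumptions.** Expected-success cut 0.90-0.99 (predictive probability at the current n). Futility cut 0.05 (predictive probability at n=500). Patients without Day 180 information at a look: 40-62. The upper figure is 500/4 = 125 per year × 180/365 ≈ 62; the lower allows for the planned imputation from earlier mRS.

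**Step 1: the plan's own figure.** The information for the log OR is I(N) = N × (2/9) × (1 − Σp̄³)/3, where p̄ is the pooled distribution and 1 − Σp̄³ = 0.866. Then I(500) = 500 × 0.2222 × 0.866/3 = 32.1 and √I = 5.66. With ln 1.7 = 0.531, the expected z is 3.005.

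- Fixed N=500, level 0.02: Φ(3.005 − 2.054) = 82.9%.
- Fixed N=500, level 0.025: Φ(3.005 − 1.960) = 85.2%.

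The plan states: "Based on simulations, this trial has 81% power for a cumulative odds ratio of 1.7 with a one-sided alpha of 0.025". A small loss from 82.9% to about 81% is what futility looks would produce.

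**Step 2: add the looks.** The score S is simulated as normal with mean θI and variance I. With a flat prior, the predictive probability of success at N is

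PP(N) = Φ{ [S·I(N)/I − 2.054·√I(N)] / √[(I(N) − I)·I(N)/I] }.

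Enrollment stops for expected success if PP(n) exceeds the success cut, and the study stops for futility if PP(500) falls below the futility cut. Enrolled patients are followed to Day 180 and tested at 0.02. Over the assumed range this gives power of about 79-81% and type I error of about 2.0-2.8%, close to the stated 81% and 2.5%.

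**Step 3: coverage at OR 1.7.** One setting in detail (40 pending, success cut 0.95, futility cut 0.05; power about 81%, type I error about 2.6%):

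| How the trial ended | Share of trials | Coverage | Contribution to misses | Mean OR |
|---|---|---|---|---|
| Expected success | 66.5% | 96.0% | 66.5 × 0.040 = 2.7% | 2.03 |
| Futility | 9.7% | 58.5% | 9.7 × 0.415 = 4.0% | 1.09 |
| Reached 500 | 23.8% | 99.0% | 23.8 × 0.010 = 0.2% | 1.49 |
| All | 100% | 93.1% | 6.9% | about 1.78 |

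Misses with the estimate too low are 4.3%, and too high 2.7%. With futility stopping removed, coverage is 94.9%. Across the assumed range it stays at about 93%. A separate run of this setting with multinomial data and fitted proportional odds models (12,000 trials) gave 93.3%. At OR 1, coverage is 94-95%.

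**Step 4: the estimate at OR 1.7** (geometric means)

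- All trials: 1.75-1.78. 1.75/1.70 = 1.03 and 1.78/1.70 = 1.05, so 3-5% high.
- All expected-success stops: about 2.0-2.1, some 20% high.
- Success stops at n=200: about 2.4-2.6, with coverage there of about 74-89%. 2.4/1.7 = 1.41 and 2.6/1.7 = 1.53.
- Success stops at n=450: 1.69-1.88.

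**Step 5: what an adjusted analysis changes** (setting of Step 3, outcomes ordered by the estimate)

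| Stop | Model OR (95% CI) | Median-unbiased OR (adjusted CI) |
|---|---|---|
| n=200 | 2.42 (1.40-4.18) | 2.36 (1.40-4.02) |
| n=300 | 1.95 (1.25-3.05) | 1.86 (1.17-2.97) |
| n=450 | 1.70 (1.18-2.45) | 1.63 (1.07-2.42) |

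**The case against.** **The thresholds are unseen.** Both documents refer the interim details to the adaptive design report, which may already contain an adjusted estimate or coverage results. This stands: 93% is a modelled figure, not one from the documents. It is, however, stable over the thresholds tried.

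**A reader might infer that an early-stopped OR is generally far too large.** The plan does not support that. It also stops for futility, where the OR comes out too low, and by n=450 the excess after a success stop is small. Even at n=200 part of the excess is not caused by the looks. I(200) = 12.8, so success there requires an OR of at least exp(2.054/3.58) = 1.77. In a fixed 200-patient trial with true OR 1.7, the median OR among significant results is already 2.11. That is ln(2.11/1.7) = 0.216, against ln(2.4/1.7) = 0.345 to ln(2.6/1.7) = 0.425, or 51-63% of the log-scale excess.

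**A reader might also infer that 93% coverage means the interval is too narrow after a success.** It does not. Expected-success stops taken together cover about 94-96%; poor coverage after a success stop is confined to the first look.

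**The remedy hardly moves the n=200 case.** True: 2.42 becomes 2.36 with the same lower limit. The adjustment is worth having for its overall properties and for the lower limits at later looks.

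**The OR is not named as a labeling figure.** Correct. SAP 10.4 names eight secondary analyses for possible labeling claims, and the health-economic sections rely on utilization data. No argument from label use is made here.

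**Conclusion.** The point holds in a limited form. The documents specify a fixed-N estimate and interval for a design whose N depends on the data. At the planned effect the nominal 95% interval covers about 93%, chiefly because about 10% of trials stop for futility with a mean OR of about 1.1 and coverage of about 60%. As a separate effect, success stops overstate the OR by some 20% on average, by about 40-55% at n=200, and by little at n=450. The average bias over all trials is about 3-5%.

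These sizes rest on the assumed success cut (0.90-0.99), futility cut (0.05), 40-62 patients pending and a normal approximation, checked once with fitted models. They do not show that the test is invalid: the simulated type I error is close to the stated 2.5%. The mismatch between a 95% interval and a one-sided 0.02 test is a different matter. This is a desirable improvement in reporting, not a flaw that threatens the primary conclusion.

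**What to change.** In SAP 10.1 and Protocol 10.7, add that whenever enrollment stops before 500, for success or for futility:

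1. a median-unbiased OR and a design-consistent confidence interval, computed from the adaptive-design simulation, will be reported beside the model OR and CI;
2. the ordering of outcomes used to compute them is named in advance;
3. the model OR and CI are labelled as unadjusted for early stopping.

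If the adaptive design report already contains such an adjustment, cite it in both sections instead.

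The success rule is unchanged. Power was obtained by simulation, so code should exist to build on, and SAP 17 allows a revised plan. The cost is minor extra analysis and a slightly less favourable OR after most success stops. The adjustment restores overall coverage and median-unbiasedness; it does not remove the excess conditional on stopping at n=200, which is why the labelling is also needed.

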4.3 Method of Randomization

Randomization takes place centrally through a commercially available Interactive Web Response System (IWRS). Randomization will occur in a 2:1 ratio to either MIS or MM. The treatment allocation will be balanced by Hemphill Score (0 – 2, 3 – 4) and hemorrhage location (primarily lobar, primarily deep). Once a patient is determined to meet all study eligibility criteria, the Investigator (or authorized team member) obtains the treatment assignment for that subject. Crossover is not permitted after randomization. Once a subject is randomized, the subject is

considered enrolled in the study and that subject must be followed through to the end of study or to subject's termination of consent.

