- Glasgow Coma Scale: A neurological scale which aims to give a reliable and objective way of recording the conscious state of a person for initial as well as subsequent assessment. A subject is assessed against the criteria of the scale, and the resulting points give a subject score between 3 (indicating deep unconsciousness) and either 15 (fully awake person).

The CT or MR imaging performed to provide a diagnosis of ICH will be used to determine hemorrhage volume using the $A \times B \times C/2$ method.

A CTA (or MRA) performed, as standard of care to rule out vascular malformations or aneurysm as well used to determine the presence of “Arterial Spot Sign” to identify an active bleed. If an active bleed is detected, additional CT/CTA/MRAs may be taken every 6 hours if per standard of care at institution and within 72 hours of ictus until hemostasis is confirmed.

An NIHSS and GCS score must be obtained prior to enrollment. The NIHSS score must be ≥ 6 and the GCS score ≥ 5 and ≤ 15 for inclusion in the study.

The Hemphill Score will be assigned based upon the clinical presentation and imaging.

A pregnancy test must be conducted for applicable subjects (female, < 50 years old and of child bearing potential).

If patient meets all eligibility criteria, they will be randomized 2:1 to either MIS or best MM alone. After a subject is randomized they will be considered enrolled. Randomization will be balanced using stratification based upon presenting condition (Hemphill Score) and hemorrhage location (primarily lobar vs. primarily deep). If randomized to surgery, MIS must be performed within 72 hours of the ictus.

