9.3 Subject Data Protection

Each subject will be assigned a unique subject identification number at the time of enrollment. This subject identification number will be retained throughout the study. Study sites will keep a log that notes the subject's name and corresponding subject identification number. All case report forms (CRFs) will be tracked, evaluated, and stored using only the subject ID number. No personally identifying information will be included on the case report forms.

The informed consent form will notify subjects that study monitors, auditors, and representatives of government agencies will have access to personally identifying information to ensure that data reported on the CRFs corresponds to the person who signed the consent form and the information contained in the source documentation. The patient must be informed that the data will be stored and analyzed by computer, that national regulations for handling of computerized data will be followed. Furthermore, the patients should be informed about the possibility of inspection of relevant parts of the hospital records by the Sponsor or other Health Authorities including the FDA.

10. Statistical Procedures

The primary objective of this multicenter, randomized, clinical study is to investigate the potential efficacy of MIS to improve clinical outcomes in patients with spontaneous, non-traumatic, ICH presenting within 24 hours in comparison to best MM. The primary hypothesis to be tested is that treatment with MIS will improve outcomes at 180 days as compared to the best MM group. Each eligible subject will be randomized in a 2:1 ratio to either the MIS or best MM with a balanced randomization based upon the hemorrhage location (primarily lobar, primarily deep) and Hemphill Score (0 – 2, 3 – 4). The hemorrhage location and Hemphill Score have been shown to be associated with functional outcome.^{6,10,19,25} An adaptive design approach will be utilized to allow for interim analyses and decisions on early stopping for either predicted success or failure.

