10.6 Interim Analysis

Interim data analysis of the primary efficacy and safety endpoints is planned after 200 subjects have been enrolled. Additional interim analyses will be conducted after every 50 subjects are enrolled. The interim analyses will include imputing the 180 day mRS score for subjects who do not have a 180 day score. Based on the predictive probability that the study would be a success the study may be stopped early for futility or enrollment may be stopped based on expected success. The specific details of the planned analyses are described completely in the adaptive design report.

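### The primary mRS analysis leaves out the two factors used to balance allocation: valid, but conservative and less powerful than the adjusted model already in the SAP

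*SAP*

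**What the plan says.** Protocol 6.4 describes the allocation: "Randomization will be balanced using stratification based upon presenting condition (Hemphill Score) and hemorrhage location". Protocol 4.3 and SAP 3 give the levels as Hemphill 0-2 or 3-4 and primarily lobar or primarily deep. The opening of protocol section 10 gives the reason: "The hemorrhage location and Hemphill Score have been shown to be associated with functional outcome".

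SAP 10.1, and protocol 10.7 in the same words, then set the order of the two models: "The primary analysis will be unadjusted. A secondary analysis model will include the minimization variables of Hemphill Score and hemorrhage location". Neither document explains that order.

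Success at the final analysis is judged at one-sided 0.02, within an overall one-sided error of 2.5% (protocol 10.1 and 10.7). On power, protocol 10.1 states: "This design provides 81% power for a cumulative odds ratio of 1.7 for the Day 180 mRS". The planning distribution (protocol Table 3, SAP Table 1) is marginal and is not split by stratum. The first interim look is at 200 enrolled, and protocol 10.6 adds: "Additional interim analyses will be conducted after every 50 subjects are enrolled". The stopping thresholds are in the adaptive design report, which is not among these documents.

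**The concern.** Balancing on a prognostic factor removes chance differences between the arms on that factor. The unadjusted standard error still allows for those differences, so it is larger than the true sampling variation of the estimate. The test then rejects less often than its nominal 2% under the null and gives up power under the alternative.

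The stake is efficiency, not validity. In a trial capped at 500 patients, the primary test could need more patients than necessary to reach a given power. The protocol itself asserts that the factors are prognostic, so only the strength of the effect is in doubt.

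**Working it through.** **Inputs from the documents.** N=500 maximum, allocation 2:1, cumulative OR 1.7, final one-sided level 0.02 (critical value 2.054), six outcome levels with mRS 5 and 6 merged, MM distribution 3/10/7/7/14/59%.

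**Reproducing the stated power.** For the unadjusted proportional-odds test (Whitehead), V = N × (1/3)(2/3)/3 × (1 − Σ p̄³) and power = Φ(ln OR × √V − z), where p̄ is the 1:2 weighted average of the two arms.

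- Applying OR 1.7 to the MM row gives MIS 5.0/15.3/9.6/8.8/15.6/45.8%, in line with the MIS row of the table. Once that row is rescaled from 101%, the table's own cumulative ORs are 1.65 to 1.72.
- Σ p̄³ ≈ 0.134, so V ≈ 500 × 0.0741 × 0.866 = 32.1 and √V ≈ 5.66.
- Power = Φ(0.531 × 5.66 − 2.054) = Φ(0.95) = 82.9% at fixed N=500.
- Interim looks lower this slightly. An assumed rule was used: looks at 200 to 450 every 50; success above 0.90 predictive probability; futility below 0.01; 62 patients pending, from 500 × 180/1461 days. With non-prognostic factors it gives 80.6% power and 2.5% overall error, against the stated 81% and 2.5%.

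**Unadjusted against adjusted, fixed N=500.** The adjusted model is logit P(Y ≤ k) = α_k + β·treatment + γ_H·Hemphill + γ_L·location. Prognostic odds ratios and stratum shares are assumptions: 30% Hemphill 3-4 and 60% deep in the main case. The MM margin is held at Table 3, the marginal OR is held at 1.7, allocation is in stratified blocks, and no data are missing. There were 40,000 runs per cell (SE about 0.2 points for power, less for the paired gain).

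| Assumed OR, Hemphill / location | Unadjusted power | Adjusted power | Gain | Gain with 15-50% high Hemphill |
|---|---|---|---|---|
| 1 / 1 | 82.0% | 82.1% | 0.1 | 0.1 |
| 1.5 / 1.1 | 82.1% | 82.5% | 0.4 | 0.3-0.5 |
| 2 / 1.25 | 82.5% | 83.4% | 0.9 | 0.7-1.3 |
| 3 / 1.5 | 82.8% | 85.2% | 2.4 | 1.5-2.9 |
| 5 / 2 | 83.1% | 87.7% | 4.6 | 2.8-5.5 |

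Over the last three rows, true size at nominal 2.0% is 1.1-1.8% unadjusted and 1.9-2.1% adjusted.

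**In patients.** To match the adjusted test at N=500 with 30% high Hemphill, the unadjusted test needs about 517, 532 and 562 patients in those three rows, that is 17/500 = 3%, 32/500 = 6% and 62/500 = 12% more.

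**With interim looks** (assumed 0.90 rule, 30% high Hemphill, unadjusted vs adjusted):

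| Assumed OR | Power | Mean N at OR 1.7 | Overall error |
|---|---|---|---|
| 2 / 1.25 | 80.4 vs 81.4% | 369 vs 363 | 2.5 vs 2.7% |
| 3 / 1.5 | 81.4 vs 83.6% | 367 vs 355 | 2.2 vs 2.7% |
| 5 / 2 | 82.1 vs 86.1% | 368 vs 344 | 1.9 vs 2.7% |

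The SE of the error is 0.09 points. With a success threshold of 0.95 instead, power is 81.2 vs 82.2, 82.2 vs 84.5 and 82.9 vs 86.9%, and overall error is 2.3, 2.0 and 1.7% vs 2.5, 2.4 and 2.5%.

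**Robustness.**

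- Minimization instead of stratified blocks gives 82.2 vs 83.1, 82.5 vs 84.5 and 83.2 vs 87.6%.
- If the marginal OR is defined by averaging the cumulative log odds ratios, power is 81.9 vs 82.7, 80.7 vs 83.1 and 80.0 vs 84.8%. The level moves with the definition; the gain hardly does.
- With 10% dropout in both arms and SAP 13's median fill read as a pooled model, the gains are 1.0-1.1, 2.4 and 4.4-4.7 points.

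**The case against.** The strongest reply is that nothing is broken. The unadjusted test is pre-specified, matches its power calculation and does not inflate error. The adjusted model will be reported anyway, and the SAP 10.5 subgroup models and one SAP 13 sensitivity analysis also use both factors. On this view only the label of primary is at issue. All of that is true, and it is why this is a suggestion. But the label decides which test determines success.

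The size of the gain rests wholly on assumed prognostic strength and stratum shares, and weak factors give under half a point. That stands. It also stands that, in the fixed-N table, unadjusted power does not fall as prognosis strengthens, so some of the benefit of balancing is already realised. The rest shows up as a size below 2%, which the plan does not seek.

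Adjustment has costs. The odds ratio becomes conditional: a marginal 1.7 corresponds to 1.71-1.86 within strata. The conservatism is also used up, and under the assumed 0.90 rule overall error reaches 2.7%. Both points stand and bear on the fix.

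Changing the primary test in an open-label trial, possibly after interim looks, could also be questioned. Sign-off before unblinding (SAP 1) and interim analysis by an independent statistician (SAP 15) limit this but do not remove it.

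Last, the contingency in SAP 4 for loss of equipoise would pool MM data from public trial results, where an adjusted model might not be fittable. That is a possible reason for the present choice, but neither document gives it.

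**Conclusion.** The point holds as an avoidable loss of efficiency. The test is valid, and the stated 81% is met to within one or two points, depending on how the marginal odds ratio is defined. With interim looks under the assumed 0.90 rule, adjustment gains about 1, 2 and 4 points of power for weak-to-moderate, moderate and strong prognostic factors. The fixed-N range runs from nil to 5.5 points.

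The direction is firm once the factors are prognostic, as the protocol says they are. The size is not, because the documents give no prognostic odds ratios, no stratum shares and no stopping thresholds.

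**What to change.** In SAP 10.1 and protocol 10.7, make the proportional-odds model with treatment, Hemphill stratum (0-2, 3-4) and location (lobar, deep) the primary analysis. Report the unadjusted odds ratio as supportive, and state that the primary odds ratio is conditional on the strata.

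Rerun the design simulations with the adjusted test at every look and with the planned missing-data fill, so that the 81% power and 2.5% overall error describe the test actually used. If overall error exceeds 2.5%, recalibrate the success threshold or the final level. The missing-data fill belongs in the rerun because unequal dropout affects both tests: with 15% dropout in MM and 5% in MIS, one assumed model gave a size of 2.4-3.9% unadjusted and 3.2-4.1% adjusted. Another gave 1.6-2.4% and 2.2-2.8%. No change to the imputation is proposed here.

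The timing is set by SAP 1: "The SAP will be signed off prior to unblinding". Date the change and record that those deciding had seen no comparative results.

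The cost is the rerun and any recalibration in the adaptive design report, plus an odds ratio that no longer corresponds directly to the marginal planning table. No new data or patients are needed. If the sponsor prefers the marginal odds ratio as the primary measure, the SAP should say so and give the reason.
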